### **Timeline/Timing of Procedures Participants:**

All the testing procedures will be carried out in both intra- and extra-operative sessions; these procedures are described below in the section title '*Research Testing Procedures for both -- and Extra-operative Sessions*'. Healthy controls will be studied during extra-operative session, i.e. outside the operating room.

Patients who have chosen to have surgery may participate in up to three testing sessions. These testing sessions may include a session performed during the surgery; in the operating room (intra-operative session). Some patients will undergo one session prior to surgery, and/or another session after the surgery; these studies will be performed outside the operating room (extra-operative session).

Physiological monitoring of the central nervous system (CNS) will be carried out during both intra- or extra-operative sessions. CNS monitoring in the intraoperative sessions will include recordings of single neuron activity, local field potentials from microelectrode and surface electrodes, and the EEG. CNS monitoring in the extra-operative sessions will include EEG alone. Any intra- or extraoperative session may include monitoring through EKG electrodes, EMG electrodes, accelerometers, eye position sensors, and skin conductance monitors.

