For implanting the ECoG strip, the preoperative MRI study will be used to plan the surgical target and trajectory. We will identify a point on the primary motor cortex (M1), 3 cm from the midline, based on anatomical identification of the central sulcus. The goal is to target the arm-related area of M1, slightly medial to the 'hand knob' (Yousry et al., 1997), in the same parasagittal plane as the typical entry site for placement of the subthalamic nucleus or thalamic deep brain stimulator electrodes. The location on the scalp will have a radio-opaque marker stereotactically placed on it. After drilling the frontal burr holes and opening the dura mater an eight-contact subdural electrocorticography strip (2.3 mm contacts, 1 cm spacing) will be placed on the brain surface and directed posteriorly in a parasagittal plane to provide contacts covering M1 and the primary sensory cortex (S1). In some cases, one subdural strip may be placed through both burr holes. The location of the burr holes will be determined by the selection of the safest entry point for the intended deep brain stimulator trajectory with no additional skull or scalp exposure needed for electrocorticography strip placement. The burr hole will then be sealed with a fibrin sealant after placement of the electrocorticography strip (and guide tube for microelectrode recording/deep brain stimulator lead placement).

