#### **Objective I: Sensory Processes**

In these studies the patient is presented with a sensory stimulus (pain, visual, auditory, tactile) and the response is recorded. In most cases the sensory stimulus will be applied during a cognitive tasks engaging attention or learning. All experimental protocols and variables will be under computer control and will be carried out in healthy subjects or patients undergoing functional stereotactic procedures for movement disorders or pain.

Date: February 19, 2023

Principal Investigator: [name].

Application Number: NA\_00079932

The intra-operative studies will be carried out over multiple sessions; each session will include recordings from a single neuron. In many of these sessions, painful or nonpainful somatic stimuli, and other stimuli will be presented in a single train. The painful somatic stimulus will be a cutaneous laser stimulus (Themis, Starmed Tec, Starnberg, Germany) and the non-painful stimulus will be a cutaneous electrical stimulus (DS7A, Digitimer, Hertfordshire, UK). The length of the sessions will be less than one hour and twenty minutes in total.

Analysis of the response to these stimuli will include source modeling, and is carried out to estimate the location of the cortical generator for the evoked potential, and activation resulting from that stimulus. Subsequent studies will examine sites activated in a coherent fashion during the processing of the sensory stimulus. Analysis of single neuron and LFP recordings will look for evidence of desynchronization, coherence and directed functional connectivity between different structures. The results will be interpreted as evidence of connectivity within sensory networks. All experimental protocols and variables will be under computer control.

During the testing sessions, we will also measure the salivary cortisol levels. Cortisol levels are responsive to acute stress and acute tonic pain (Zimmer et al., 2003; Dedovic et al., 2009). Subjects will be informed to not engage in moderate exercise or consume food or drink two hours before the testing sessions (Hansen et al., 2008).

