### Objective III: Sensory Processes: Behavioral Tasks

These tasks will include attention tasks and a learning task which involves the painful and nonpainful stimuli, as described above under *Sensory Processes: Sensory stimulation*, including Heat Stimuli (Laser -2 and Thermode-3), and Electrical Stimuli-7. Attentional protocols will be carried out in one session, often with presentation of a painful (laser, thermode, or electrical), and a nonpainful (electrical or thermode) stimulus presented in a single train in random order. The subject is instructed to either: i) count or ii) push buttons in response to the painful stimulus (attention to pain), or the non-painful stimulus (distraction from pain) or both, as presented in random order and counterbalanced across patients. In three other tasks, a single train will consist of: i) only nonpainful stimuli which the patient counts, ii) only painful stimuli which the patient counts and iii) only painful stimuli while the patient performs a cognitive task, e.g. reading for comprehension.

Some subjects in both categories will be involved in protocols for classical conditioning or learning, which occurs when a neutral conditioned stimulus (CS+, a light or sound) is paired with an unconditioned aversive or appetitive (reward) stimulus (US). In the case of aversive conditioning, the US might be the painful cutaneous laser, thermode, or electrical stimulus, while in appetitive conditioning it might be a reward of one dollar. As measures of psychological variables, we propose to administer psychological questionnaires including depression, anxiety and PTSD scales.

Under Objective I extra-operative studies will often be carried out over a two hour session during which painful and nonpainful stimuli will be presented in a single train. During the extra-operative conditioning protocol, two or three sessions may be carried out on different days. Within each session there will be rest periods and between two and six separate trials with either attentional or conditioning tasks. The length of the intraoperative sessions will be less than one hour in length.

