## 7. Study Statistics

This is a single institution, long-term exploratory study to understand forebrain networks of human sensory processing and motor control. Specifically Objective I will address cortical and subcortical networks of sensory signaling and processing, while Objective II will address the cortical and subcortical networks involved in motor control.

Due to the exploratory nature of the study, all outcome data will be collected regardless of data type such as electrophysiological responses, or timing, or the questionnaires related psychological function. In general, data will be summarized using descriptive statistics and graphical techniques. Within and between-subjects comparisons will use paired and unpaired analysis, respectively. Longitudinal outcomes or repeated measures will be considered and possibly be analyzed using generalized linear model. Correlation coefficient or concordance correlation coefficient will be used to estimate correlation between two outcomes.

The outcome measures for the three objectives are indicated below:

Primary and secondary outcome variables:

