### ***Objective I:***

Under Objective I we will determine functional connectivity between structures at which single neuron and LFP responses occur in response to painful laser stimuli. Secondary outcome variables will address cognitive processes related to sensory stimuli and the networks which subserve them. These networks will be defined by measures of functional connectivity between electrode sites such as correlation, coherence, and causal (directed) interactions.

Network characteristics will be estimated by measures of connectivity at the time of laser stimuli between sites such as correlation, coherence, functional connectivity, and causal interactions.

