### ***Objective II and III:***

Our primary outcome variables will identify the functional connectivity within networks of cortical and subcortical structures which subserve movement. We will determine functional connectivity between structures activated during actual and imagined movement. Recordings will be made of single neuron and LFP activity in the basal ganglia, thalamus and cortex during actual and imagined movements.

Our secondary outcome variables will identify the functional connectivity within networks of cortical and subcortical structures which subserve movement disorders. We

Date: February 19, 2023

Principal Investigator: [name].

Application Number: NA\_00079932

will determine functional connectivity between structures activated during disordered movement. We will also determine the effects of tDCS on single and multiunit activity in the recorded subcortical structures. Recording and analysis techniques will be similar to those under the primary outcome of this objective.

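### Section 7 does not say how correlation within a patient is handled: the only model tentatively named for repeated measures is a generalized linear model, which in its standard form treats neurons and sites from one patient as independent

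*Combined protocol and SAP*

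**What the plan says.** Section 7 (Study Statistics) calls the study exploratory and says that data will in general be described and graphed. Two sentences concern comparisons. The first is "Within and between-subjects comparisons will use paired and unpaired analysis, respectively". The second is "Longitudinal outcomes or repeated measures will be considered and possibly be analyzed using generalized linear model".

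The outcomes listed after this lie below patient level. For Objective I, "These networks will be defined by measures of functional connectivity between electrode sites such as correlation, coherence, and causal (directed) interactions". For Objectives II and III, the outcomes are connectivity based on single-neuron and field-potential recordings, and "We will also determine the effects of tDCS on single and multiunit activity in the recorded subcortical structures".

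Section 4 describes how many such records one patient can give. Under Objective I: Sensory Processes, "The intra-operative studies will be carried out over multiple sessions; each session will include recordings from a single neuron". Under Motor Control, the tests are run at a maximum of 7 recording sites.

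Neither Section 7 nor any other part of the document mentions a random effect, estimating equations, a working correlation, a clustered variance, a per-subject summary or the unit of analysis.

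**The concern.** Neurons or sites recorded in one patient share that patient's disease, anatomy, arousal and recording conditions, so their values are correlated. A generalized linear model without an extension has no term for this. It takes the number of records as the amount of independent information.

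The main contrasts are within a patient: painful against nonpainful stimuli, actual against imagined movement, activity with and without tDCS. For these the direction of the error is not fixed. If the effect is the same in every patient, ignoring the shared patient level makes the test conservative. If the effect differs between patients, the test can be clearly anti-conservative. A reader of a reported network finding could not tell which case applied, because the plan does not state the unit or the correlation model.

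**Working it through.** The plan gives no alpha, power, effect size or intraclass correlation for these comparisons, so there is no figure of its own to reproduce. What follows is an illustration.

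**Inputs**
- From the plan: m = 7 sites per patient, the stated maximum in the motor tests.
- Assumed: n = 10 patients; two-sided 5% alpha; two conditions at each site; normal data; m = 3 as an alternative; intraclass correlation ρ = 0.1, 0.3 or 0.5; share f of the paired-difference variance lying between patients = 0 (common effect), 0.1 or 0.3.

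**Set-up.** Each value is a patient intercept (variance ρ) plus a residual (variance 1 − ρ). A patient-specific condition effect with variance v is added, half to each condition with opposite sign. Then f = v / [v + 2(1 − ρ)], so v = 2(1 − ρ) f / (1 − f).

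**Formulas.** Multiply the variance of the mean difference by nm:
- true value: T = m v + 2(1 − ρ)
- value assumed by the independence model: N = 2(1 + v/4)
- approximate true size: 2[1 − Φ(1.96 / √(T/N))]

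**Common effect (f = 0).** T/N = 1 − ρ, whatever m is: 0.9, 0.7 and 0.5. The sizes are 3.9%, 1.9% and 0.6%. Simulation with 7 sites gives 4.0%, 2.3% and 1.0%.

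**Varying effect, two cells in full**
- m = 7, ρ = 0.1, f = 0.3: v = 1.8 × 0.3/0.7 = 0.771; T = 5.4 + 1.8 = 7.2; N = 2(1 + 0.193) = 2.386; T/N = 3.02; 1.96/1.737 = 1.128; size 25.9%.
- m = 3, ρ = 0.5, f = 0.1: v = 1.0 × 0.1/0.9 = 0.111; T = 0.333 + 1.0 = 1.333; N = 2.056; T/N = 0.649; 1.96/0.805 = 2.434; size 1.5%.

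All cells, true size of the independence model as formula / simulation:

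| ρ | f | 7 sites | 3 sites |
|---|---|---|---|
| 0.1 | 0.1 | 11.2% / 11.6% | 6.7% / 7% |
| 0.1 | 0.3 | 25.9% / 26.6% | 13.6% / 14% |
| 0.3 | 0.1 | 7.3% / 7.8% | 3.9% / 4% |
| 0.3 | 0.3 | 20.9% / 22.2% | 9.7% / 10% |
| 0.5 | 0.1 | 3.5% / 4.4% | 1.5% / 2% |
| 0.5 | 0.3 | 14.5% / 15.8% | 5.4% / 6% |

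Placing the whole patient effect in one condition changes N to 2(1 + v/2) and lowers the highest cells. In the first worked cell N = 2.771, T/N = 2.60, 1.96/1.612 = 1.216, and the size is 22.4%.

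**One value per patient.** A one-sample t-test on the 10 patient means of the differences is exact for normal data. Simulation gives 4.8% to 5.2%.

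**The case against.** The strongest reply is that nothing here is a fixed analysis. Section 7 only raises repeated measures as something to consider and names a model that might be used. The phrase does not rule out the usual extensions by random effects or estimating equations. The section is mainly descriptive and sets no alpha or decision rule. It already names paired analysis for within-subject comparisons, which with one pair per subject holds its size. Nearly all inputs to the illustration are assumed, and several cells are at or below 5%.

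Most of this stands, and it limits the point. Three stronger readings that a reader might infer are not supported:
- *The plan commits to an invalid test.* It does not; the wording is tentative.
- *The paired tests will use sites or neurons as pairs.* With 7 sites this would have a size of about 12% at f = 0.1 and 24% at f = 0.3. But the plan never says so, and pairing by subject is the more natural reading.
- *Every repeated element in Section 4 adds clustered replicates.* The possible testing sessions for a surgical patient include only one in the operating room. The others record EEG without neurons or field potentials. The trials within an extra-operative session are largely different tasks or phases. The contacts on the cortical strip are not tied to any stated analysis. Only neurons and sites carry the point.

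What the reply does not remove is the gap itself. The objectives speak of testing hypotheses, and Section 7 plans comparisons within and between subjects. Exploratory status does not correct a standard error. Paired analysis does not cover more than two occasions, such as the three saliva samples. If an extension of the model was intended, the plan needs to say so.

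**Conclusion.** The point holds as an under-specified method. The only model named for repeated measures ignores within-patient correlation in its standard form, and nothing in the plan supplies the missing part, although several neurons and up to 7 sites can come from one patient. Followed literally at neuron or site level, it gives standard errors that can be wrong in either direction.

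Under the stated assumptions the true size is about 1-4% with a common effect. With a varying effect it is about 4-27% at 7 sites and about 2-14% at 3 sites. Only the maximum of 7 sites comes from the plan, so neither the size nor the direction of the error is established for this study. In particular, it cannot be concluded that its results will carry too many false positives.

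Severity: minor.

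**What to change.** In Section 7, for comparisons meant as inference:
- State that the subject is the independent unit, and give the observation level (trial, neuron, site or site pair) of each outcome.
- Replace the generalized linear model with a generalized linear mixed model with subject random effects, including subject-level condition effects where the data support them. Alternatively, use generalized estimating equations clustered on subject with a small-sample correction.
- Where there are too few patients to fit either, reduce the data to one summary value per subject and condition and use the paired or unpaired tests already named.

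The cost is two or three sentences and slightly more analysis work. The per-subject summary needs no new software, and no new data are required. Intervals will be wider for some contrasts, and may be narrower where the independence model would have been conservative.

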### ***Objective I:***

Under Objective I we will determine functional connectivity between structures at which single neuron and LFP responses occur in response to painful laser stimuli. Secondary outcome variables will address cognitive processes related to sensory stimuli and the networks which subserve them. These networks will be defined by measures of functional connectivity between electrode sites such as correlation, coherence, and causal (directed) interactions.

Network characteristics will be estimated by measures of connectivity at the time of laser stimuli between sites such as correlation, coherence, functional connectivity, and causal interactions.

### ***Objective II and III:***

Our primary outcome variables will identify the functional connectivity within networks of cortical and subcortical structures which subserve movement. We will determine functional connectivity between structures activated during actual and imagined movement. Recordings will be made of single neuron and LFP activity in the basal ganglia, thalamus and cortex during actual and imagined movements.

Our secondary outcome variables will identify the functional connectivity within networks of cortical and subcortical structures which subserve movement disorders. We

Date: February 19, 2023

Principal Investigator: [name].

Application Number: NA\_00079932

will determine functional connectivity between structures activated during disordered movement. We will also determine the effects of tDCS on single and multiunit activity in the recorded subcortical structures. Recording and analysis techniques will be similar to those under the primary outcome of this objective.

### **Data Sharing**

Specifically for the Auditory Stimulation and Speech Testing intraoperative studies described above, we wish to share a subject specific descriptive and electrophysiology data set with the University of Pittsburgh Medical Center (Dept. of Neurosurgery) as part of an NIH Brain Initiative funded study (U01 NS098969 - Subthalamic and corticosubthalamic coding of speech production, PI – [name]). This study is additionally administered under the University of Pittsburgh IRB # PRO13110420 (Intraoperative Brain Recordings in Movement Disorders Patients).

The data transfer will utilize the REDCap research database system in a shared study database. Subject records will include: subject age and sex, diagnosis code and a brief clinical history including age of disease onset, DBS target, pre-op UPDRS III motor examination results, pre-op neuropsychological examination results (as per the summary above), pre-op speech analysis measures, pre-op medications, 6 month post-op UPDRS III motor examination results, 6 month post-op neuropsychological examination results, 6 month post-op speech measures, 6 month post-op medications, and medical imaging (CT, MRI, fluoroscopy) results will be recorded in the database.

Additionally, deidentified cortical strip ECoG, audio voice responses, and subcortical single and multi-unit activity and LFP will be shared for these select subjects derived from the approximate 30 minute intraoperative auditory and speech testing protocol. The encrypted, HIPAA compliant data base for this transfer will utilize the Pitt-Box (University of Pittsburgh sponsored) application.

## **8. Risks**

As in previous studies, the main risk of intra-operative tests is identified as the fatigue associated with additional testing at several recording sites during the localization procedure. Therefore, the main risks of the operation are associated not with the research tests, but with the standard surgical procedure.

In addition, the somatic sensory, motor, and psychological tests may be applied during extra-operative testing in all patients and healthy subjects. These tests are associated with relatively minor risks during both intra-and extra-operative testing. These risks are listed below by the category of testing. The tests, or combinations of tests, below in this section, and in the section above on 'Research testing procedures ...', are numbered using the same system as is used in the Consent.

Date: February 19, 2023

Principal Investigator: [name].

Application Number: NA\_00079932

None of these risks has resulted in a patient injury in the many years in which these research procedures have been performed for prior studies. All subjects will have the option to withdraw from the protocol at any time without penalty.

**Risks for Research Testing Procedures for both Intra- and Extra-operative Sessions:**

Somatic sensory research testing:

Sensory stimuli, such as the laser, mechanical, nonpainful electrical stimulation, and ice water (see above section on '*Research Testing Procedures ...*'), are applied so that the patient can remove themselves from the stimulus at any time. In addition, the thermal stimulators (laser and contact thermode) are computer controlled, with built in controls to prevent injury. The laser stimuli may lead to a grade 1 burn (sunburn) manifest by skin freckling lasting for a few days.

The ischemia test lasts for about three minutes. In the ischemia test, the investigator will stand at the patient's side and will be prepared to deflate the cuff at any time.

Biological Specimen Sampling:

There is a low risk of infection or bruising from the blood sampling. We reduce this risk by using sterile needles, alcohol scrub, applying pressure to your arm after removing the needle, and using state certified phlebotomists experienced in conducting blood draws. An additional low risk possibility is that a participant might experience light-headedness associated with the needle stick.

There are no known risks to providing a saliva sample.

Motor Research Testing:

During Torque motor testing the patient will be able to release the manipulandum of the Torque Motor at any time. Unexpected movements of the torque motor will be aborted by an accessible switch which will disable the machine and which may be pushed by anyone in the room.

Psychological Research Testing:

These are minimal risk procedures. In conditioning studies, the CR will be extinguished by presenting the CS+ without the US (extinction) to normalize the CR. Numerous imaging studies of classical aversive conditioning and psychological interviews and questionnaires have been carried out safely at universities across the United States in psychiatric patients and in healthy controls (reviewed in (Rauch et al., 2006; Phelps, 2006)).

The psychiatric-structured interviews and questionnaires pose a small time burden and a minimal emotional burden or risk to participants. Participants may be uncomfortable answering some questions. They will be instructed that they may choose not to answer questions they do not want to. The seriousness of any risk would be minimal, particularly since any emotional burden would occur in the context of an interview with a practicing psychiatrist or a clinical psychologist, who could

Date: February 19, 2023

Principal Investigator: [name].

Application Number: NA\_00079932

intervene if there were any symptoms during the interviews. There is a small risk of breach of confidentiality if data security measures were compromised.

Transcranial direct current stimulation:

Weak direct currents can be applied non-invasively, transcranially and painlessly. Such application leads to transient changes in corticomotor excitability that is fully reversible. There are no known risks of percutaneous, transcranial DC stimulation of the brain, other than mild local discomfort at the electrode sites. In the current published studies on humans, the following objective safety data were reported:

No significant elevations in temperature of the electrodes.

No demonstrable changes in the skin underlying electrode placement after a stimulation period similar to the one proposed in this protocol.

Mild itching sensation in the absence of pain. This never led to stopping a study in any of the previous reports.

No change in serum neuron-specific enolase (NSE, marker for neuronal damage) in 5 subjects immediately and 1 hour after exposure to 13 min of 1 mA anodal DC to motor cortex.

No changes in diffusion weighted or contrast-enhanced MRI and in EEG after exposure to tDCS.

Nitsche et al. have studied several hundred subjects so far without reporting any side effects apart from a slight itching under the electrode and a short phosphene if the stimulation was switched on or off abruptly. In his own work and in his review of the modern literature, Priori found no evidence or mention of adverse effects using this technique. Additionally, several months' use of this technique at NIH in approximately 30 subjects (Drs. [name] and [name]) was performed in the absence of any deleterious side effects. All of these reports are in accordance with our experiences in a recently performed study by [name] in elderly healthy volunteers and chronic stroke patients. Furthermore, the NINDS IRB approved recently a protocol of Drs [name] and [name] (03-N-0116) to apply tDCS repetitively (8 sessions) in Parkinson patients. Both anodal and cathodal tDCS have been successfully applied during 20 minutes in 12 stroke patients, including 2 patients with cortical stroke, without any adverse effects

Finally, a review paper discussed the safety of tDCS in humans. tDCS application over motor and non-cortical areas in 102 subjects (in healthy individuals, migraine patients, post-stroke patients, and tinnitus patients) revealed the most common adverse effect after tDCS was a mild tingling sensation, followed by fatigue, then a light itching sensation under the stimulation electrodes. Not as common, but mentioned, were headache, nausea, and insomnia. Poreisz et al. concluded that tDCS is associated with very minor adverse effects in healthy humans and patients with varying neurological disorders

In addition, other recent publications have shown that it is also possible to use 2mA intensities without significant risk or complications (current density of 0.095 mA/cm^2 and delivered a total charge of 0.086 C/cm^2.) over the cerebellum or prefrontal cortex for 15 minutes without any

Date: February 19, 2023

Principal Investigator: [name].

Application Number: NA\_00079932

complications. Finally, in an editorial by Bikson, unpublished data is reported using current densities of 25.46 A/m^2 for 20 minutes with minimal sensation and no skin damage.

An animal study (rat) (Liebetanz et al., 2009), investigated the safety limits of extended transcranial direct current stimulation. Fifty-eight rats received single cathodal stimulation at 1–1000  $\mu$ A for up to 270 min through an epicranial electrode. Histological evaluation was performed 48 h later. A threshold estimate was calculated from volumes of DC-induced lesions. Brain lesions occurred at a current density of 142.9 A/m^2 for durations greater than 10 min. For current densities between 142.9 and 285.7 A/m^2, lesion size increased linearly with charge density; with a calculated zero lesion size intercept of 52400 C/m^2. Brains stimulated below either this current density or charge density threshold, including stimulations over five consecutive days, appeared the same as nonstimulated controls. The results of these systematic animal studies provide an estimate of a safety threshold for deleterious DC effects. With respect to the charge density, the upper limit used for these proposed human intraoperative studies is lower by two orders of magnitude.

One perceived limitation for the use of tDCS intraoperatively in subjects undergoing DBS lead placement is the resulting modification of current flow by the presence of surgical burr holes. Modeling studies can provide insight into how skull defects would affect current flow through the brain. Based on modeling results modifying the stimulation current intensity and changing the electrode location or electrode type can compensate for the effects (Datta et al., 2010). In the case of a craniotomy, there is a relatively highly conductive fluid pathway for current entering the brain, but it is highly dependent on the craniotomy position relative to the electrode montage used with tDCS. A small defect under the anode electrode leads to current flow in the cortex restricted to locations directly under the defect. A similar sized defect placed between the electrodes does not significantly alter current the flow pattern in comparison with a healthy head with no defect ( Datta et al., 2010).

The tDCS electrodes in this study will be placed at least 3 cm from the closest burr hole.

The psychological and neuropsychological tests are administered by pencil and paper or by a structured interview with a practicing psychiatrist or clinical psychologist.

